7. INTERVENTION(S)

a) Drug/Substance 1

	Ţ
Name of drug/substance to be used	Prucalopride
Formulation and route of administration for study	1mg prucalopride tablets will be encapsulated in opaque capsules.
Dose and route of administration for study	1mg oral dose, daily
Duration of treatment for study	Seven days
Licence status of this drug/substance	Prucalopride is a licensed drug.
Usual Indication	Prucalopride is indicated for the symptomatic treatment of chronic constipation in adults.
Usual Dose	The usual dose given is 2 mg once daily with or without food, at any time of the day.
Usual duration of treatment	Prucalopride can be administered long- term, although the efficacy of the drug in the treatment of constipation has only been established up to 3 months.
Where will drug/substance be sourced from?	The drug will be sourced from the Oxford Pharmacy Store, Kennington in the form of 1mg film-coated tablets.
Where will drug/substance be stored?	Prucalopride will be stored within the Neurosciences Building at the Department of Psychiatry. It will be stored at room temperature in a locked cupboard, which is suitable for drug storage.
How will drug/substance be dispensed?	Prucalopride will be dispensed from the Neurosciences Building by a study medic or nurse.
How will the drug/substance be prepared by the researchers for use in this study?	Prucalopride will be encapsulated by trained clinical trial support staff using our Standard Operating Procedure (see protocol APPENDIX H: ENCAPSULATION STANDARD OPERATING PROCEDURE (SOP)).

b) Drug/Substance 2 (or placebo)

	,
Name of drug/substance to be used	Lactose Placebo
Formulation and route of administration for study	Placebo tablets will be encapsulated in opaque capsules.
Dose and route of administration for study	One capsule taken orally, daily
Duration of treatment for study	Seven days
Licence status of this drug/substance	N/A
Usual Indication	N/A
Usual Dose	N/A
Usual duration of treatment	N/A
Where will drug/substance be sourced from?	Placebo tablets will be sourced from HSC (www.hsconline.co.uk).
Where will drug/substance be stored?	Placebo tablets will be stored within the Neurosciences Building at the Department of Psychiatry. It will be stored at room temperature in a locked cupboard, which is suitable for drug storage.
How will drug/substance be dispensed?	Placebo tablets will be dispensed from the Neurosciences Building by a study medic or nurse.
How will the drug/substance be prepared by the researchers for use in this study?	Placebo tablets will be encapsulated by trained clinical trial support staff using our Standard Operating Procedure (see protocol APPENDIX H: ENCAPSULATION STANDARD OPERATING PROCEDURE (SOP)).

8. SAFETY

a) Definitions

Adverse Event (AE)	Any untoward medical occurrence in a participant to whom a substance has been administered, including occurrences which are not necessarily caused by or related to that substance.
Adverse Reaction (AR)	An untoward and unintended response in a participant to a substance, which is

	related to any dose administered to that participant.
	A causal relationship between the administered substance and an AE is at least a reasonable possibility, i.e. the relationship cannot be ruled out.
	All cases judged by either the reporting medically qualified professional or the Sponsor as having a reasonable suspected causal relationship to the study intervention qualify as adverse reactions.
Serious Adverse Event (SAE)	 A serious adverse event is any untoward medical occurrence that: results in death is life-threatening requires inpatient hospitalisation or prolongation of existing hospitalisation results in persistent or significant disability/incapacity consists of a congenital anomaly or birth defect. Other 'important medical events' may also be considered serious if they jeopardise the participant or require an intervention to prevent one of the above consequences. NOTE: The term "life-threatening" in the definition of "serious" refers to an event in which the participant was at risk of death at the time of the event; it does not refer to an event which hypothetically might have caused death if it were more severe.
Serious Adverse Reaction (SAR)	An adverse event that is both serious and, in the opinion of the reporting Investigator, believed with reasonable probability to be due to one of the study treatments, based on the information provided.
Suspected Unexpected Serious Adverse Reaction (SUSAR)	A serious adverse reaction, the nature and severity of which is not consistent with the information about the medicinal product set out in its summary of product characteristics (SmPC).

b) Reporting Procedures for Serious Adverse Events or Reactions

A serious adverse event (SAE) occurring to a participant should be reported to CTRG and the Medical Sciences IDREC where, in the opinion of the Principal Investigator, the event was 'related' (resulted from administration of any of the research procedures) and 'unexpected' (the type of event is not listed in the protocol as an expected occurrence). Reports of related and unexpected SAEs should be submitted within 15 days of the Principal Investigator becoming aware of the event. For fatal and life-threatening SUSARs, this will be done no later than 7 calendar days after the Sponsor or delegate is first aware of the reaction. Any additional relevant information will be reported within 8 calendar days of the initial report.

c) Safety of Participants

What level of baseline screening will take place for this study?

All participants will undergo a Screening Visit to ensure only eligible participants take part. The following will be recorded at baseline screening:

- Demographic information (age [years, months], years in full-time education)
- Number of cigarettes smoked per day, units of alcohol consumed per week, caffeinated drinks consumed per day
- Current and prior use of drugs (to exclude for drug use in the three months prior to the study)
- SCID-V interview (Structured Clinical Interview for DSM-V) to probe for current or past psychiatric illness
- Beck Depression Inventory (BDI)
- Eysenck Personality Questionnaire (EPQ)
- State and Trait Anxiety Inventory (STAI)
- Positive and Negative Affect Schedule (PANAS)
- Snaith-Hamilton Pleasure Scale (SHAPS)
- National Adult Reading Test (NART)
- Edinburgh Handedness Inventory
- Side effect questionnaire
- Visual Analogue scales (VAS)

To ensure it is safe to administer the drug to the participant, the following will be recorded:

- Weight, height, and BMI
- Medical history (including family psychiatric history)
- Details of current and past medication
- Urine pregnancy test (female participants only)

To ensure it is safe for the participant to undergo fMRI scanning, the following will be administered

MRI safety form to ensure no contraindication to MRI scanning

Participation in prior studies will be recorded to exclude for individuals who have used the same/similar emotional processing tasks.

Provide details about the safety monitoring of participants and the staff/researchers carrying this out

During the week of drug/placebo administration, participants will be advised not to drink alcohol and not to carry out activities requiring full alertness if they are aware of any impairment. During this week, a researcher will phone up the participant on day 2 and day 4 to check that there are no concerns. Participants will have the 24-hour contact phone number of a member of the study team and be encouraged to get in contact if they have any concerns or queries during the study week, or if their health status changes. The named researcher will in turn contact a qualified medical doctor if necessary.

Give details on the medical cover required and who will provide this cover

A medical doctor who is part of the research team will review the screening and make a final judgment about including participants in the study. A qualified medical doctor will be contacted if a participant expresses concern to a named researcher regarding side effects or health status changes during the study week.

Will the participants' GP be informed about their participation in the study? In not, please justify

Participants' GPs will not be informed about their participation in the study. Seven days of low-dose prucal pride (1mg) administration is not regarded as a clinically significant intervention and is not expected to have any impact on participants' health or wellbeing. We are excluding participants who are pregnant, breastfeeding or who have any medical conditions for whom the study would not be suitable.

What is your planned procedure if an incidental finding is suspected?

The detailed images obtained from MRI scanners, while not suitable for clinical diagnosis, may on rare occasions identify unexpected structural abnormalities. If an abnormality is noted on the structural scan of a healthy volunteer, the "WIN/OCMR/OHBA Standard Operating Procedure – Dealing with Research Neuroimaging Incidental Findings" will be strictly followed.

Participants will be screened to exclude those with past or current psychiatric symptoms and Best Practice Guidance (BPG) 08 (Psychological distress) will be followed in order to ensure best practice in situations where participants with psychological distress are identified. The guidance in this document around confidentiality and researcher training will also be adhered to.

If an incidental finding has clinical implications, what action will you take?

During the consent process, subjects would be informed of our standard procedure for incidental findings ("WIN/OCMR/OHBA SOP — Dealing with Research Neuroimaging Incidental Findings"). This outlines the process of involving a dedicated local hospital NHS consultant clinician in the case of a suspected abnormality, although it is stressed that a routine inspection and reporting of research scans is not carried out. In the case of a suspected abnormality, the Principal Investigator would alert our Contact Radiographer who, if appropriate (i.e. not a simple artefact) would independently inform the Contact Neurologist. They would in turn obtain the opinion of the Contact Neuroradiologist, and decide on the appropriate course of action, which might involve contact with the individual at the earliest opportunity and possible further investigation, including a hospital (NHS) diagnostic scan. This would all take place within the NHS framework and in communication with the volunteer's GP.

If a researcher has concerns that a volunteer may have an undiagnosed psychiatric condition that is causing distress (identified during the screening visit or following review of the mood-related questionnaires), CUREC guidance (BPG08) will be followed. The researcher will seek advice from the Principal Investigator who may discuss the symptoms in greater detail with the volunteer and/or offer the opportunity to speak with a senior clinical researcher. If the volunteer indicates that they are not currently receiving support and it is felt necessary, they will be encouraged to contact their General Practitioner.

Please give details of departmental SOPs (if any) that will be followed in the case of an incidental finding

During the consent process, participants would be informed of our standard procedure for incidental findings [APPENDIX I: WIN/OCMR/OHBA STANDARD OPERATING PROCEDURE (SOP) – DEALING WITH RESEARCH NEUROIMAGING INCIDENTAL FINDINGS].

d) Ethical Considerations

Will you include any vulnerable participants (e.g. children, elderly)?	Yes 🗌	No X
If yes, please describe how they are defined as vulnerable and detail any CUREC approved procedures or guidance that you feel apply.		
Will taking part in the research put participants under any particular burden and/or	Yes X	No 🗌
risk?		
If yes, describe how this will be mitigated.		

a) There is a theoretical risk that a participant may have an adverse reaction to the study drugs. Participants will be informed of the potential side effects prior to taking the medication. To minimise risk, the participants' general health will be assessed before being accepted into the study. They will be excluded from the study if they are currently taking any psychoactive medication or if they have any known contraindications to taking the drug (see exclusion criteria).

The most frequently reported adverse reactions associated with prucalopride 2mg therapy are headache (17.8%) and gastrointestinal symptoms (abdominal pain (13.7%), nausea (13.7%) and diarrhoea (12.0%)). Other side effects associated with prucalopride are decreased appetite, dizziness, vomiting, flatulence, fatigue, and gastrointestinal sounds. The terminal half-life of prucalopride is about 1 day. There is less information about the side effect profile in healthy volunteers rather than patients, or after short-term prucalopride 1mg administration, although a single 1mg dose of prucalopride was well tolerated in our previous healthy volunteer study. The potential side effects are clearly stated in the Participant Information Sheet and researchers will discuss these with participants as part of the informed consent procedure.

The drug has been tested in healthy volunteers in pharmacokinetic studies and to establish interactions with other drugs (for example, we know that prucalopride does not affect the pharmacokinetics of the oral contraceptive (9)).

To minimise the risk associated with side effects, participants will be contacted on days 2 and 4 of the study week by a named researcher to check there are no concerns. All participants will have 24-hour contact details of a named researcher who they can contact during the study period. The named researcher will in turn contact a qualified medical doctor if necessary. In order to limit the risks associated with fatigue, during the week of prucalopride/placebo administration, participants will be advised not to drink alcohol, and not to carry out activities requiring full alertness if they are aware of any impairment.

If judged necessary by the medical lead, the randomisation code will be broken for that individual by the medical supervisor and the participant will be advised to stop taking the medication and withdrawn from the study.

b) While most people do not experience discomfort in an MRI environment, the enclosed space of the scanner can potentially feel uncomfortable. Discomfort from lying still for a long period of time will be minimised with comfortable padding and positioning. Whilst in the scanner, participants will be able to use the alarm button if they wish to communicate with the operator or to interrupt scanning. People with a history of severe claustrophobia would be excluded from participation in the study. All participants will be introduced carefully to the scanner and informed that they can terminate the scan session at any stage, should they wish to do so. Once inside the scanner, participants will be able to indicate if they wish the scanning to cease by squeezing a bulb placed in their hand, or by requesting verbally. As the MRI scanner is noisy, participants will be given earplugs to minimise the noise.

MRI is a safe, non-invasive technique, which does not involve ionising radiation. Risks associated with the

magnetic field will be removed by excluding potential participants with ferromagnetic obje (e.g., metal implants, vessel clips, shrapnel injuries) or with implanted devices, which may be magnet (e.g., heart pacemakers). All people entering the scanning room will complete an N questionnaire just before entering the scanner.	oe damaged	by the
Will the research involve deliberate deception of participants?	Yes	No X
If yes, justify why deception is used, describe deception and debriefing process, and	_	
include debriefing documents in the application		
Will any procedures affect your own physical and/or psychological safety as a	Yes 🗌	No X
researcher?		
If yes, describe how this will be mitigated.		
Does your research raise issues relevant to the Counter-Terrorism and Security Act (the	Yes 🗌	No X
Prevent Duty), which seeks to prevent people from being drawn into terrorism?		
If yes, please say how you plan to address any related risks. Please see advice on this on		
our Best Practice Guidance Web Page .		
Please give details of any other ethical and/or safety considerations		

9. STATISTICS AND ANALYSIS

Do you have a statistical plan?	Yes X	No 🗌
If no, please justify.		
The IBM SPSS statistical software will be use to analyse all behavioural data.		
Demographic and baseline measures will be analysed using independent t-tests.		
Mood, anxiety, and side effect measures will be analysed using repeated measures analysis of variance (ANOVA).		
Behavioural task results will be analysed using between-groups analysis of variance (ANOVA).		
Any significant interactions will be followed up using simple main effect analyses. When assumptions of equality of variances are not fulfilled, the Greenhouse-Geisser procedure will be used to correct the degrees o freedom.		
Analysis of fMRI endpoints will be completed using the FSL software package.		
Number of Participants		
50 healthy volunteers (25 per group)		

Have you done a sample size calculation?	Yes 🖂	No 🗌
If yes, please give details below		
If no, please give details to indicate you have considered the implications the selected		
sample size will have on the study outcome		
We will be using the Emotion Test Battery, which is a well validated set of emotional proces sensitive to antidepressant effects. On the facial expression recognition task, one of the magnitudes is accuracy at recognising fearful facial expressions and a sample size of 25/group power to detect changes of the magnitude of those we have seen in a previous antidepres volunteer study [drug mean 10.64 (SD 9.77) vs. placebo mean 3.36 (SD 5.96) from Harmer Psych; ref 6].	nain outcom would give sant healthy	e e 0.9 y
Analysis of Outcome Measures		
Data analysis will take place at the University of Oxford, Department of Psychiatry and will be undertaken by the research team under the supervision of the Principal Investigator. All data will be analysed using a between-groups analysis of variance (ANOVA). Analysis of fMRI endpoints will be completed using the FSL software package.		·

Withdrawn participants' data will not be included in the analysis.

The primary outcome measures are performance (accuracy and reaction time) in a computer-based task of facial expression recognition (FERT), and performance on the auditory verbal learning task AVLT, compared between drug and placebo groups. Secondary to this is the amygdala and hippocampal BOLD fMRI response to emotional faces and novel vs. repeated scenes respectively, reward sensitivity on the PILT, and number of positive and negative words correctly categorised, recalled, and recognised on emotional memory tasks. The tertiary outcome measures are reaction times to fearful vs. happy faces on the FDOT, BOLD fMRI response during resting state, performance (accuracy and reaction time) on the OMT task of visual short term memory, and relative/global cerebral blood flow using arterial spin labelling, all compared between those receiving drug and placebo.

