case, if more than four weeks has elapsed, another screening visit will be performed to ensure participants are still eligible.

Randomised participants will be given seven days of the drug to take home, as well as full instructions of how and when to take them. The study has a double blind design thus neither the researchers nor the participant will know whether prucalopride or placebo is given.

During the week of drug/placebo administration, participants will be advised not to drink alcohol and not to carry out activities requiring full alertness, such as driving, if they are aware of any impairment. During this week, a researcher will phone up the participant on day 2 and day 4 to check that there are no concerns. Additionally, participants will receive a text message every day reminding them to take the study medication. They will have the 24-hour contact phone number of a member of the study team and be encouraged to get in contact if they have any concerns or queries during the study week, or if their medication or health status changes.

Subsequent Visits

1. Research Visit One (approximately 1.5 hours) on day 6 of prucalopride/placebo administration. This visit will involve an fMRI scan taking place at the Oxford Centre for Human Brain Activity (OHBA), which is part of the Department of Psychiatry on the Warneford Hospital site.

On arrival, participants will complete the MRI screening form (APPENDIX D) once more to ensure it is still safe for them to undergo fMRI scanning.

Participants will complete the following questionnaires before and after the fMRI scan:

- State Anxiety Inventory (STAI-S)
- Positive and Negative Affect Schedule (PANAS)
- Side effect questionnaire
- Visual Analogue Scales (VAS)

The scan itself will include:

- Structural scan
- Emotional faces task
- Memory task
- Resting state
- Arterial spin labelling
- Physiological recordings including pulse, respiration, and skin conductance recorded using a pulse meter, respiration bellows and electrodes strapped by Velcro to fingertips.
- Eye tracking
- 2. Research Visit Two (approximately 2 hours) on day 7 of prucal opride/placebo administration. This visit will involve administration of behavioural tasks measuring emotional and non-emotional cognitive processing.

Participants will complete the following questionnaires before and after the behavioural tasks:

- State Anxiety Inventory (STAI-S)
- Positive and Negative Affect Schedule (PANAS)
- Side effect questionnaire

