4.1 Summary of study design

This is a double-blind placebo-controlled parallel group experimental medicine study, which will be conducted at the University of Oxford, Department of Psychiatry. The site will recruit 50 healthy volunteers between the ages of 18 and 40. Study staff will identify potentially eligible participants from the general public, who will be made aware of the trial through advertisements on local information websites (e.g. Daily Info, Oxford University Gazette), newspapers, local magazines, on the radio and on the lab webpage, Facebook page and Twitter account, and in universities and other public places. Each participant will attend 3 study visits in total which will be conducted at the Department of Psychiatry. After having confirmed initial study eligibility by phone or email (Pre-Screening), participants will be invited to the department for the Screening Visit (2 hours). If this visit qualifies them as eligible, participants will be recruited into the study and will be invited for visits 2 and 3 on two consecutive days, no later than 1 month after the Screening Visit. Visit 2 will be the Research Visit 1 (~1.5 hours), and visit 3 will be the Research Visit 2 (~3 hours), where behavioural and neural parameters will be obtained. Self-report clinical symptom severity (mood, anxiety and side effects) will be measured on all visits, and before and after testing on visit 2 and visit 3.

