7.2 Data Cleaning

Data cleaning of the behavioural data and fMRI data will be performed prior to unblinding. Cleaning of behavioural data (i.e. accuracy and reaction times) from the emotional processing tasks will be checked to ensure the tasks have been completed appropriately by

a clinical data analyst at P1vital Products. Specifically, trials where participants show unusually low response times (< 200ms) or high response times (> 6000ms) will be excluded. Similarly, participants who show abnormally low accuracy on the emotional tasks will be excluded (<50% correct responses on the FERT and FDOT). Cleaning of behavioural data from the non-emotional cognition tasks will be performed by the research team, coordinated by the Principal Investigator. Extreme outliers will be excluded from each group on a per task basis. The fMRI data cleaning will be performed by the research team, with guidance from BRC Imaging Support. fMRI data will be visually checked for excessive movement and other artefacts such as signal drop out, as well as to ensure all required data files are present. Formal MRI quality assessment will be undertaken using the MRIQC package (https://mrigc.readthedocs.io/en/stable/index.html), with data considered for rejection if falls outside the normal range of values in the derived image quality metrics. Following collection of all data to be analysed, a final data inclusion meeting will be held with the Principal Investigator prior to unblinding. This will review data quality and confirm exclusion of data from specific tasks. Data will be excluded on a per task basis—that is, a participant may have data excluded for one task, but have all other data available for analysis. Analyses of each task will then be performed on all randomised subjects who have data available for that task.

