8.1 Analysis Populations

The population used for the analysis of data in this study will be:

- All randomised subjects for non-fMRI data, except for withdrawn participants who will not be included in the analysis.
- As per protocol set for fMRI data (criteria: fMRI data available). fMRI data will not be available for all participants per se depending on need to exclude / withdrawal.

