8.4.1 Demographic data and psychometric data

To assess changes in subjective mood and anxiety before and after prucalopride/placebo administration, mixed model ANOVAs will be performed with time as a within-subjects factor and group as a between-subjects factor on STAI-S, PANAS, and VAS ratings. Post hoc analyses using independent samples t tests will follow up any significant interactions. A generalised linear model will be used to analyse side effects.

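### Repeated measures ANOVA for STAI-S, PANAS and VAS drops any non-withdrawn participant who misses one modelled rating, although the SAP population includes them; a linear mixed model would keep them

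*Protocol*

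**What the plan says.** **Method.** Protocol section 9: "Mood, anxiety, and side effect measures will be analysed using repeated measures analysis of variance (ANOVA"). SAP 8.4.1 is more specific: "mixed model ANOVAs will be performed with time as a within-subjects factor and group as a between-subjects factor on STAI-S, PANAS, and VAS ratings". Significant interactions are followed by independent-samples t tests. The levels of time are not listed. Side effects are handled separately in the SAP ("A generalised linear model will be used to analyse side effects"), so this point concerns STAI-S, PANAS and VAS only.

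**Occasions.** SAP 4.1 says that self-reported mood, anxiety and side effects "will be measured on all visits, and before and after testing on visit 2 and visit 3". The schedule in SAP 6.1 agrees, and Protocol section 6 has the same scales at screening and around each research visit; for the scan visit, "Participants will complete the following questionnaires before and after the fMRI scan".

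**Population and missing data.** SAP 8.1 defines the set as "All randomised subjects for non-fMRI data, except for withdrawn participants who will not be included in the analysis". SAP 8.2 has one sentence, which excludes withdrawn participants. SAP 7.2 adds an availability condition written for tasks: "Analyses of each task will then be performed on all randomised subjects who have data available for that task". No section says what happens when a participant who remains in the study misses a mood or anxiety rating.

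**The concern.** A mixed-design ANOVA with time as a within-subjects factor, as the standard SPSS repeated measures procedure fits it, needs a complete row for each participant. This is a property of the method; the documents do not mention it. One missing cell removes the person and all their valid ratings.

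The model in SAP 8.4.1 would then use fewer people than the population in SAP 8.1, by a rule that appears nowhere in the plan. The cost is precision on the time-by-group interaction, and that test decides whether the follow-up t tests are run. Two tables in the same report could also rest on different people without explanation.

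**Working it through.** The plan gives no figure for missing ratings, and its sample-size calculation concerns fear recognition, so there is no stated number to reproduce. The missing rates, the correlation and the missingness mechanisms below are assumptions.

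**1. Number of occasions.** Screening 1, scan visit 2, testing visit 2: 1 + 2 + 2 = 5 (SAP 4.1 and 6.1; Protocol section 6).

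**2. Loss per gap.** If k of 50 participants each miss only the after-scan rating, a five-level complete-case analysis keeps 50 − k people and discards 4k valid ratings:
- k = 1: 49 people kept, 4 ratings discarded
- k = 3: 47 kept, 12 discarded
- k = 5: 45 kept, 20 discarded

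**3. Share dropped under independent gaps.** With missing rate q per rating and m modelled occasions, the share dropped is 1 − (1 − q)^m.
- m = 5: q = 0.01 gives 1 − 0.99^5 = 4.9% (about 2 of 50); q = 0.03 gives 1 − 0.97^5 = 14.1% (about 7 of 50)
- m = 2: q = 0.01 gives 2.0% (1 of 50); q = 0.03 gives 5.9% (about 3 of 50)

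**4. Precision.** Contrast: mean of the four on-treatment ratings minus screening, weights (−1, ¼, ¼, ¼, ¼), 25 per arm, unit SD, equal correlation r = 0.5.
- Variance per participant: (1 − r) × (1 + 4 × 1/16) = 0.5 × 1.25 = 0.625
- Complete data: SE of the group difference = √(2 × 0.625 / 25) = 0.2236 SD
- k per arm lacking both scan-visit ratings, complete cases only: SE is multiplied by √(25 / (25 − k)). k = 1: 1.021 (0.2282). k = 4: 1.091 (0.2440)
- Same gaps, all available ratings, generalised least squares with the same covariance: k = 1: 1.003 (0.2243). k = 4: 1.014 (0.2268)

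The excess is thus 2-9% under the ANOVA against 0.3-1.4% under a mixed model.

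**5. Bias under informative gaps.** Suppose the drug raises anxiety by 0.5 SD.
- *Missingness depends on the observed pre-scan rating* (anyone above +1.5 SD leaves). By the normal tail, 1 − Φ(1.5) = 6.7% of placebo and 1 − Φ(1.0) = 15.9% of drug participants are lost. In simulation the time-by-group contrast is 0.489 with full data, 0.471 with complete cases and 0.489 with a mixed model. The shift of about 0.02 SD is removed.
- *Missingness depends on the unobserved after-scan rating*, same cut-off. The contrast is about 0.499 with full data, 0.480 with complete cases and 0.471 with all available ratings. The mixed model does no better.

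**The case against.** The strongest case against is that the plan describes a standard method for supportive measures, and that gaps should be few: the ratings are taken at attended visits, and the two research visits fall on consecutive days. Most of this stands, and it limits the size of the point.

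A reader might infer more than the documents support:

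- *That volunteers who stop the scan fall out of the anxiety comparison.* Protocol section 8 says participants are "informed that they can terminate the scan session at any stage, should they wish to do so". It does not say that they then leave the visit or skip the after-scan forms. SAP 8.1 expects some fMRI data to be unavailable, but rejecting a scan removes no questionnaire, and withdrawn participants are excluded by an explicit rule and replaced.
- *That the SAP promises all randomised subjects.* It excepts withdrawn participants.
- *That five levels of time are certain.* SAP 8.4.1 speaks of change before and after administration and lists no levels, which is why a two-level range is given as well.
- *That the anxiety result would be seriously biased.* In the first scenario of step 5, the pre-scan difference among those retained falls from 0.50 to 0.35 SD. The plan does not call for that estimate: a follow-up t test at the pre-scan occasion needs only that rating, which these people have. The planned contrast moves by about 0.02 SD.

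It could also be said that the SAP's wording already means a linear mixed model. SAP 8.4.1 names no random effect, covariance structure or estimation method. SAP 8.4.2 also lists tasks described as mixed model ANOVAs in a table of repeated measures ANOVAs, so the two terms appear to be interchangeable there.

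What survives is the mismatch between population and model, the missing rule for a missed rating, and the avoidable loss of precision.

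**Conclusion.** The point holds as a minor one. The ANOVA specified for STAI-S, PANAS and VAS would remove non-withdrawn participants whom SAP 8.1 includes, and nothing in SAP 8.2 covers them. The 5-14% range for participants dropped rests on independent gaps at 1-3% per rating with five modelled occasions; with two occasions it is 2-6%. The 2-9% inflation of the standard error rests on 1-4 per arm lacking both scan-visit ratings and on a correlation of 0.5. If no ratings are missed, nothing is lost.

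The dependable gain from a mixed model is precision and consistency with the stated population. It protects against bias only when missingness depends on ratings that were observed. It does not touch losses through withdrawal, which the plan excludes by rule. STAI-S, PANAS and VAS are not among the SAP 6.2 endpoints, so neither the primary nor the secondary conclusions depend on this.

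**What to change.** In SAP 8.4.1, and in Protocol section 9 for mood and anxiety:

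- List the occasions that form the levels of time.
- Replace the ANOVA for STAI-S, PANAS and VAS with a linear mixed model fitted by REML (SPSS MIXED): group, occasion as a categorical factor, and group by occasion, with a stated within-participant covariance, using every available rating from every non-withdrawn participant.
- State in SAP 8.2 that a missed rating does not remove a participant's other ratings, and report the number of missing ratings per group and occasion.

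The cost is wording and a different procedure in software already named; no new data are needed. With complete data and compound symmetry the model gives the same test as the ANOVA. The small downside is that a covariance structure must be fixed in advance. If the ANOVA is kept, the least change is to say that it is a complete-case analysis and report how many are excluded per group.
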